- Surface Mechanomyography: Three triaxial accelerometers adhered to the skin using adhesive tape on the chest, upper back, and thigh will be used to assess shivering.
- Resting Energy Expenditure (thermogenesis): Expired oxygen, carbon dioxide, and ventilation will be collected from the whole-body calorimetry and used to calculate thermogenesis using the abbreviated Weir formula (5).
- International Physical Activity Questionnaire: Participants will complete this form to self-report and quantify their level of physical activity.
- Health history and demographics questionnaire: Participants will complete a health history questionnaire to ensure they meet the inclusion and exclusion criteria.
- Health history update questionnaire: Upon each visit to the laboratory participants will complete the health history update questionnaire to ensure no changes in their health history has occurred.
- Infrared Thermography Images: An infrared thermography camera will be used to measure skin temperature in the supraclavicular (i.e., collar bone) region. This provides a non-invasive estimate of brown adipose tissue activation (6).
- PAR-Q+: Participants will complete this questionnaire to ensure they meet the inclusion and exclusion criteria.
- 3-Day Dietary Log: Myfitnesspal.com (Under Armour) is a dietary log that will be used to quantify the type and amount of food and fluid that participants consume 3 days prior to each study visit.
- Body Composition: Participants will have their body composition measured using DEXA.
- Whole Blood Collection: 15 mL of whole blood will be obtained from an antecubital vein at pre-mirabegron/placebo and at 15 minutes post protocol using standard aseptic techniques defined by the World Health Organization.
- Fecal Sample Collection: Participants will be given fecal collection kits (DNA Genotek) and will be given verbal instructions from the collection kit directions on how to obtain samples as well as the pamphlet that contains these directions the after the study visits of Specific Aim 1. Participants will be instructed to obtain samples from their first bowel movement after each study visit.

Timeline of Procedures

Specific Aim 1

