empty water immersion tank. Then they will be instrumented for the measurement of heart rate (3-lead ECG), blood pressure (brachial artery auscultation), core temperature (rectal thermistor), and indices of shivering (surface mechanomyography using triaxial accelerometers at 3 anatomic sites (chest, upper back, and thigh), oxygen consumption via ventilation and expired gases, and the bedside shivering assessment scale). Thermal perceptions will be assessed using Likert scales for thermal discomfort and thermal sensation. Following 10 minutes of resting baseline measurements, infrared thermography will then be used to measure skin temperature of the supraclavicular fossa as an estimate of brown adipose tissue activation and thermal perceptions will be assessed. The participants will then ingest either mirabegron (100 mg) or a placebo tablet. The dose of mirabegron will be determined from the results of Specific Aim 1. The dose of mirabegron that elicits the greatest increase in thermogenesis in Specific Aim 1 will be used in Specific Aim 2. The measurement of supraclavicular fossa skin temperature (infrared thermography) and thermal perceptions will be assessed every 10 minutes prior to the progressive cold-water challenge. After 30 minutes of seated rest, pre-immersion measurements of heart rate, blood pressure, core temperature, shivering, and thermal perceptions will be conducted and an infrared thermography image will be taken. Then, the water immersion tank will be filled up to the participant's neck with 35°C (95°F) water. Heart rate, blood pressure, core temperature, and shivering indices will be continuously measured. Infrared thermography and thermal perceptions will be obtained every 5 minutes throughout the progressive cold-water challenge. The water will be cooled at a rate of 12°C per hour until the water temperature reaches 10°C (50°F), the participant can no longer tolerate the cold water, or core temperature reaches 35.5°C (95.9°F). This is 0.5°C higher than the clinical definition of hypothermia. Also, the risks associated with hypothermia are core body temperature-dependent and not dependent on time (7). Upon completion of the progressive cold water challenge, the water in the tank will be rapidly emptied. Participants will gently towel dry and will be able to don a circulating warm water perfused suit and/or use a mylar blanket to reestablish core temperature. If participants complete the informed consent/screening visit and all study visits, we expect that they will spend a total of ~11 hours in the study.

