- Acute Mirabegron ingestion: Mirabegron ingestion in the population that will be studied is deemed safe (3) and will be prescribed under the direction of our study physician, [name]. The doses that will be used in this study have mild cardiovascular (heart rate and blood pressure) effects that are associated with the dose of mirabegron (e.g., the greater the dose of mirabegron, the greater the cardiovascular response (2, 3). Acute oral administration of 200 mg of mirabegron has been shown to increase heart rate by ~8 beats per minute and systolic blood pressure by ~10 mmHg with no changes in diastolic blood pressure (2). These increases in heart rate and blood pressure are far below the heart rate and blood pressure

responses associated with moderate to heavy exercise intensities that are achieved in healthy 18-40 year old men and women.

- Head Out Water Immersion: Water temperature during Specific Aim 2 will be perceived as being cold and rectal temperature will decrease and participants might shiver. We will constantly monitor rectal temperature during the study visits for Specific Aim 2. Any risks are reversible with removal from the cold water and warming with warm water perfused suits and/or mylar blankets, which are located in the laboratory. The protocol will be immediately terminated if core temperature drops to 35.5°C or if the participant does not want to continue. This safety cutoff is 0.5°C higher than the clinical definition of hypothermia and we don't expect core temperature to drop to 35.5°C. For instance, 60 minutes of 15°C water immersion decreased core temperature less than 1°C (8). Another study safely had participants sit in 10°C (50°F) water up to the mid-sternum for 90 minutes and core temperature only decreased to 36.2°C (9). In a case study, 88 minutes of full body immersion in crushed ice lowered core temperature from 37.6°C to 37.0°C (10). Also, the risks associated with hypothermia are core body temperature-dependent and do not appear to be dependent on time (7).
- Whole blood sample: Participants will likely experience discomfort during venous blood draws and in rare circumstances may feel lightheaded or faint. This risk will be minimized by the venipuncture always occurring in the semi-recumbent or supine position. There is a rare risk of infection following venous blood draws. This risk will be minimized by blood draws only being conducted by trained laboratory personnel.

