12.0 Statistical Considerations

Specific Aim 1

Power Analysis: Using data from Loh et al. (2) we expect to observe an effect size (δ) of 0.90 for the comparison of resting energy expenditure in the placebo condition versus 200 mg of mirabegron. Given this effect size, 10 participants will be needed to achieve a power of 0.99 with an alpha level set at 0.05. To account for possible attrition, we plan on recruiting up to 30 participants.

Statistical Approach: We will compare the primary (i.e., thermogenesis) and secondary (i.e., core temperature, skin temperature, heart rate, blood pressure, indices of shivering, thermal perceptions, and infrared thermography images) dependent variables using mixed effects ANOVA (i.e., mirabegron dose x time) followed by Tukey's post hoc procedure if a significant interaction or main effect is found from the ANOVA analyses. We will also calculate the thermogenesis area under the curve for each dose of mirabegron. These values will be compared using repeated measures ANOVA followed by Tukey's post hoc procedure if a significant main effect is found from the ANOVA analysis. We will also perform correlation analyses to determine the relation between body composition and our primary and secondary dependent variables. The alpha level will be set at $P < 0.05$ for all analyses.

Specific Aim 2

Power Analysis: Similar to Specific Aim 1 and the data from Loh et al. (2), we expect to observe an effect size (δ) of 0.90 for the comparison of rectal temperature in the placebo condition versus the mirabegron condition. Given this effect size, 10 participants will be needed to achieve a power of 0.99 with an alpha level set at 0.05. To account for possible attrition, we plan on recruiting up to 30 participants.

Statistical Approach: The primary (i.e., core temperature deflection point) and secondary (i.e., onset of shivering inflection point) dependent variables from the mirabegron and placebo trials will be compared using paired t-tests to determine if mirabegron improves cold-water immersion tolerance. Mixed effects ANOVA will be used to compare the remaining dependent variables between conditions (i.e., mirabegron vs. placebo) and across time. If a significant

interaction or main effect results from the ANOVA analyses, we will use the Holm-Sidak post hoc test to determine where differences exist. The alpha level will be set at $P < 0.05$ for all analyses.

Specific Aim 3

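### Aim 2: infrared images of the supraclavicular fossa taken during neck-deep immersion are, as the procedure is written, not a valid estimate of brown adipose tissue activation and should stay out of the Aim 2 ANOVA

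*Combined protocol and SAP*

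**What the plan says.** The general procedure list in section 7.0 defines the measure for all aims: "An infrared thermography camera will be used to measure skin temperature in the supraclavicular (i.e., collar bone) region". It names no other site. The Aim 2 timeline in the same section repeats the site and its purpose: "infrared thermography will then be used to measure skin temperature of the supraclavicular fossa as an estimate of brown adipose tissue activation".

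Imaging before immersion takes place in the empty tank. There is a baseline image before dosing, and then: "The measurement of supraclavicular fossa skin temperature (infrared thermography) and thermal perceptions will be assessed every 10 minutes prior to the progressive cold-water challenge". A pre-immersion image follows at the end of 30 minutes of seated rest.

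After that, "the water immersion tank will be filled up to the participant's neck with 35°C (95°F) water", and during cooling "Infrared thermography and thermal perceptions will be obtained every 5 minutes throughout the progressive cold-water challenge". Section 9.0 confirms the position with its heading on head-out immersion. Towel drying appears only after the challenge, once the tank has been emptied.

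For the analysis, section 12.0 (Aim 2) assigns the deflection point and the shivering inflection point to paired t-tests and continues: "Mixed effects ANOVA will be used to compare the remaining dependent variables between conditions (i.e., mirabegron vs. placebo) and across time". Infrared is not named in that sentence. It is named in the corresponding Aim 1 paragraph.

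**The concern.** The measure needs a camera view of exposed skin whose temperature reflects heat from the tissue beneath it. Dry air in Aim 1 and the empty tank in Aim 2 allow that. Water at neck level does not obviously allow it, because the collar bone region is then under water or at the water line. What the camera sees is either the bath surface or skin wetted and cooled by the bath.

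The bath temperature is imposed by the protocol and follows the same schedule in both conditions. A series that mainly tracks it would show a marked time effect and carry little information about the drug. Brown adipose tissue activation is the mechanism that section 1.0 offers for the thermogenic effect, so a reader could take a flat comparison between conditions as evidence that the mechanism fails in cold water. A chance difference, for example from water level or posture, could equally be taken as support for it.

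**Working it through.** The plan states no figure that depends on this point, so there is nothing to reproduce. The check sets the passages side by side and counts the images.

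**Site, depth and timing**

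| Item | What the plan gives | Place |
|---|---|---|
| Imaging site | Supraclavicular fossa | 7.0, procedure list and Aim 2 timeline |
| Water level | Up to the neck | 7.0, Aim 2 timeline |
| Imaging during immersion | Every 5 min | 7.0, Aim 2 timeline |
| Exposing, raising or drying the site for an image | None described | 7.0 |
| Drying | Only after the tank is emptied | 7.0, Aim 2 timeline |

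The water line relative to the clavicle is not given, so there are two cases.
- *Fossa submerged.* Water is opaque to thermal infrared. This is general physics, not a statement in the documents. The camera records the water surface.
- *Fossa at the water line.* The skin is wet and lies next to the bath. The reading mixes skin and bath temperature in unknown proportion.

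In neither case is the reading the dry-skin temperature obtained before immersion.

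**Number of images affected**
- Inputs from the Aim 2 timeline: start 35°C, end 10°C, cooling 12°C per hour, one image per 5 min.
- Longest cooling time: (35 − 10) / 12 h = 2.083 h = 125 min.
- Images per visit: 125 / 5 = 25 intervals, so 25 + 1 = 26 images counting time 0.
- Two visits: 2 × 26 = 52 images per participant.
- Images before immersion, per visit: 1 pre-dose plus 10, 20 and 30 min after ingestion = 4, taking the 30-minute image as the pre-immersion image.
- Share affected: 26 / (26 + 4) = 87%.

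These are upper bounds. A session also stops if the participant cannot tolerate the cold or if core temperature reaches the stated limit.

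**Imposed change in the bath**, from 35 − 12 × (minutes / 60):

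| Minutes | 0 | 30 | 60 | 90 | 120 | 125 |
|---|---|---|---|---|---|---|
| Water, °C | 35 | 29 | 23 | 17 | 11 | 10 |

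The background against which any drug signal would have to be read therefore moves by up to 25°C.

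**Timing of the unaffected images.** They end about 30 min after ingestion. Section 1.0 puts the plasma peak at 3-4 h, that is 180-240 min. The usable window closes at least 180 − 30 = 150 min before the peak.

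**The case against.** The strongest reply is that no planned conclusion rests on these images. Sections 2.0 and 3.0 list infrared thermography under Aim 1 only. Aim 2 asks about core temperature and shivering, and the section 5.0 summary of Aim 2 monitoring does not mention infrared. This stands, and it limits the point to an ancillary measure.

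Three stronger readings are tempting, and the documents do not support them.
- *That a brown adipose tissue signal is impossible to obtain.* The water line is not specified relative to the clavicle, and the laboratory may expose and dry the site without having written this down. What the text shows is that no such step is planned.
- *That the condition difference must be near zero whatever the drug does.* That would follow only if the fossa were fully submerged. Exposed wet skin could give a degraded or confounded reading that keeps some drug signal. The documents give no figure for the bias.
- *That the plan explicitly analyses these readings.* Section 12.0 refers only to the other Aim 2 variables. Inclusion is the natural reading, because infrared is named as a dependent variable for Aim 1 and the Aim 2 study calendar schedules it at both visits, but it remains an inference.

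It can also be objected that keeping only the early images invites a misreading of its own, since they precede peak exposure. This is correct, and the fix has to say so.

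**Conclusion.** The point holds in a limited form. As written, the Aim 2 immersion images (up to 26 per visit, 52 per participant) are not a valid estimate of brown adipose tissue activation. They record water, or wet skin strongly influenced by a bath that falls by up to 25°C. The pre-dose and empty-tank images are not affected. Neither are the core temperature deflection point and the shivering inflection point, nor their paired t-tests.

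The conclusion assumes that no undocumented exposing and drying step exists, that neck-deep water puts the fossa at or below the water line, and that water blocks thermal infrared. That the readings enter the ANOVA is probable but not stated. The size of any distortion in the condition contrast cannot be derived from the documents. The change is worth making because it is cheap and prevents an invalid reading in either direction.

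**What to change.** - **Section 7.0, Aim 2 timeline:** end the infrared series with the pre-immersion image. Keep thermal perceptions every 5 minutes during the challenge. The water level does not change.
- **Section 12.0, Aim 2:** name infrared explicitly, exclude immersion images from the mixed effects ANOVA, and limit the comparison to the pre-dose and empty-tank images.
- **Section 12.0, interpretation:** state that these images end about 30 minutes after ingestion, before the 3-4 hour plasma peak cited in section 1.0, so a null is not evidence of no activation. State also that Aim 2 makes no claim about brown adipose tissue activation during immersion, and that Aim 1 assesses it in 20°C air only.
- **Alternative:** if the laboratory does keep the fossa exposed and dry for imaging, write that step into section 7.0 and treat the immersion images as descriptive only.

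The cost is a wording change and, under the main option, less work per visit. The downside is that Aim 2 gives up any statement on brown adipose tissue during immersion, which the procedure as written could not support.

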3.0 Outcome Measures/Endpoints**3.1 Primary Outcome Measures****Specific Aim 1:**

Thermogenesis (i.e., resting energy expenditure) and thermogenesis area under the curve during the protocol. Thermogenesis will be measured using whole body indirect calorimetry, calculated using the Weir formula (5), will be measured every 30 minutes during the 6 hour protocols. Area under the curve for thermogenesis will be calculated to reflect the cumulative effect of mirabegron over time.

Specific Aim 2:

Core temperature deflection point during the progressive cold-water immersion challenge. Core temperature will be continuously measured using rectal thermistors. The point at which core temperature begins to fall (i.e., deflection point) will be identified using Prism 8 software by plotting core temperature vs. water temperature.

Specific Aim 3:

Gut microbiota phylotypes, fecal mirabegron concentration, and serum mirabegron concentration will be measured from samples obtained during the study (serum samples: pre-mirabegron/placebo and following 6 h of mild cold exposure; fecal samples: first bowel movement following 6 h of mild cold exposure). Samples will be assessed using bacterial DNA extraction and purification, polymerase chain reaction, and MinION analysis as well as metabolomics.

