Specific Aim 2: This is a randomized, double-blind, placebo-controlled, cross-over experimental design. Participants will be asked to complete 3 visits to the laboratory; one informed consent/screening visit and 2 study visits. During the informed consent/screening visit, participants will complete the informed consent, eligibility criteria will be presented, resting blood pressure and heart rate (derived from the blood pressure measurement) will be measured, and participants will complete the following questionnaires: IPAQ, PAR-Q, and Health History Questionnaire. During the study visits, participants will undergo baseline measurements (described in detail in Section 7.0) followed by ingesting either a placebo or one dose of mirabegron (100 mg) prior to entering our water immersion tank. Mirabegron will be prescribed by our study physician, [name] (Department of Emergency Medicine, Indiana University Health). The dose of mirabegron that will be used for Specific Aim 2 is dependent on our findings from Specific Aim 1. The dose of mirabegron that elicits the greatest increase in thermogenesis in Specific Aim 1 will be used for Specific Aim 2. A second set of baseline measurements will be made and then the water immersion tank will then be rapidly filled with 35°C (95°F) water. The temperature of the water will be progressively lowered by ~12°C every 60 minutes until the water temperature reaches 10°C (50°F) or until the participant can no longer tolerate the cold or if rectal temperature reaches 35.5°C (95.9°F). Participants will be continuously monitored for rectal temperature, indices of shivering, skin temperature, heart

rate, blood pressure, and thermal perceptions (described in detail in Section 7.0). This design will allow us to determine if mirabegron improves cold water immersion tolerance.

Informed Consent/Screening Visit: Obtain informed consent. Screen potential participants by inclusion and exclusion criteria. Obtain Health History Questionnaire, PAR-Q+, and IPAQ and resting heart rate and blood pressure. Perform body composition assessment with DEXA.

Study Visits 1-2
 The order of placebo and mirabegron (100 mg) will be randomized between Study Visits 1-2. All study procedures will be identical between Study Visits. For specific study protocol and data collection procedures, please see Sections 7.0 and 8.0

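### Aim 2 has no rule for an immersion that ends before the deflection or shivering point occurs, so the paired t-test result can depend on when immersion stopped

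*Combined protocol and SAP*

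**What the plan says.** Sections 5.0 and 7.0 (Specific Aim 2) start immersion at 35°C and cool at 12°C per hour. Immersion ends at the first of three events: water at 10°C, "the participant can no longer tolerate the cold water", or core temperature at 35.5°C.

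Section 3.1 defines the primary endpoint: "The point at which core temperature begins to fall (i.e., deflection point) will be identified using Prism 8 software", and it does this "by plotting core temperature vs. water temperature". The endpoint is therefore a water temperature. Section 3.2 defines the shivering endpoint on another scale, as the core temperature just before shivering starts.

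For both points, Section 12.0 states that the "dependent variables from the mirabegron and placebo trials will be compared using paired t-tests to determine if mirabegron improves cold-water immersion tolerance". Mixed effects ANOVA is kept for the remaining variables.

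Two other statements come near the question without answering it. Section 11.0 allows data gathered before a withdrawal to be used, and Section 12.0 recruits up to 30 to allow for attrition. Neither says what value, if any, a completed visit contributes when the point did not occur before immersion ended.

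**The concern.** A paired t-test needs an observed value from both visits. If a participant leaves the water, or the water reaches 10°C, before core temperature turns down, that visit shows only that the point lies at some colder temperature. The analyst must then drop the pair or enter the stop as if it were the point. The plan chooses neither. Both choices select or truncate data for a reason tied to the endpoint.

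Non-occurrence is plausible on the protocol's own account. Section 9.0 does not expect core temperature to reach 35.5°C, so the 10°C limit and intolerance are the expected ways for a visit to end. Section 9.0 also treats shivering as possible rather than certain.

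At stake is the single primary comparison of Aim 2. An unplanned choice, made after the data are seen, could hide a real delay or produce part of one.

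**Working it through.** **The plan's own figures.** The documents give no rate of non-occurrence, so there is none to reproduce. The Aim 2 power statement is 0.99 with 10 participants at effect size 0.90. Reading 0.90 as mean difference over SD of differences, a two-sided paired t-test at 0.05 has power 0.717 with 10 pairs and 0.997 with 30. That mismatch is a separate matter; these values serve here only as a baseline.

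**Length of the ramp.** (35 − 10)/12 h = 2.08 h = 125 min. Water is below 15°C only for the last (15 − 10)/12 h = 25 min, and no hold at 10°C is described.

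**Which stops can remove which point.** The 10°C limit and intolerance can come before deflection or shivering. The 35.5°C stop cannot come before deflection, because core temperature must already have begun to fall; it could come before shivering.

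**Assumed inputs (not in the documents).** The endpoint is degrees of cooling below 35°C (maximum 25), with SD 4°C in each condition and within-participant correlation 0.5. The SD of differences is 4 × √(2 × (1 − 0.5)) = 4, so an effect size of 0.90 is a true shift of 0.90 × 4 = 3.6°C. Where intolerance acts, its SD is 4°C, it is correlated about 0.8 between a participant's visits, and placebo deflection averages 20°C water.

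**Check by hand, 10°C limit only.** P(point not reached) = 1 − Φ((25 − mean)/4). With placebo deflection at 15°C water, the means are 20 and 23.6. Placebo: 1 − Φ(1.25) = 11%. Mirabegron: 1 − Φ(0.35) = 36%.

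**Simulated estimates of the 3.6°C shift (1,000,000 pairs per row).**

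| Setting | Missing, placebo / mirabegron | Complete pairs | Stop used as point |
|---|---|---|---|
| 10°C limit only, placebo deflection at 21°C | 0.3% / 3% | 3.46 (96%) | 3.55 |
| same, 18°C | 2% / 14% | 3.19 (89%) | 3.36 |
| same, 15°C | 11% / 36% | 2.73 (76%) | 2.81 |
| same, 13°C | 23% / 56% | 2.37 (66%) | 2.21 |
| Intolerance not affected by drug, mean stop 11°C | 6% / 19% | 3.23 (90%) | 3.20 |
| same, mean stop 17°C | 30% / 54% | 2.85 (79%) | 2.09 |
| Drug shifts tolerance by 3.6°C, 17°C on placebo | 30% / 30% | 3.60 (100%) | 3.60 |
| Drug shifts tolerance by 7.2°C, 17°C on placebo | 30% / 12% | 4.05 (113%) | 4.32 |
| True effect zero, drug shifts tolerance by 3.6°C, 17°C on placebo | 30% / 12% | 0.46 | 0.72 |
| same, 14°C on placebo | 15% / 5% | 0.26 | 0.31 |

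The rows with a 3.6°C effect and shifted tolerance omit the 10°C limit. Adding it gives complete-pair estimates of 3.56 and 4.05.

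**Power, 10°C limit only.** With placebo deflection at 15°C, 61% of pairs remain and the effect size falls to 0.78. Power is about 0.87 with 30 recruited (18 pairs) and 0.34 with 10 (6 pairs). With deflection at 21°C, 97% remain and the effect size is 0.88. Power is then 0.996 with 30 recruited and 0.70 with 10.

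**Does a censored analysis do better?** In a separate set of runs with the same SD and shift, complete pairs gave 2.7 to 3.8 and using the stop as the point gave 2.1 to 4.1. The two gave 0.4 to 0.7 when the true effect was zero. A censored-normal paired model gave 3.5 to 3.75, and about 0 under no effect, including some settings with stops correlated with deflection. It is not proof against every such link. With a same-visit correlation of 0.5 and a mean stop at 17°C not moved by the drug, it overshot to about 4.2 (4.2/3.6 = 117%), against about 2.9 for complete pairs.

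**The case against.** The strongest reply is that the documents do not show the problem will be common. Section 9.0 cites people kept for 60 min in 15°C water and for 90 min in 10°C water to mid-sternum. Those exposures differ from this ramp, but they are the only tolerance evidence in the plan and do not suggest early exits. If deflection comes near 21°C water, the 10°C limit alone removes about 3% of pairs. Recruiting up to 30 also leaves room for lost pairs. All of this stands, and it is why no expected size is claimed. Extra recruits restore power, however; they do not remove bias.

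A second reply is that a censored analysis assumes the stop carries no further information about the point, and feeling too cold may well be related to deflection. That also stands. It calls for a sensitivity analysis and a table of stop reasons. It does not favour dropping or capping, which also fail when the stop is informative.

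A reader might infer that the planned test must be biased toward zero, and is therefore merely conservative. The documents do not support that. Sections 5.0 and 12.0 look for an effect of mirabegron on tolerance. If tolerance moves as much as deflection, the bias disappears; if it moves more, the effect is inflated.

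**Conclusion.** The gap is real. Aim 2 compares two points that may not occur with a test that needs both to be observed, and it states no rule for the visits where one is missing. The direction of bias in the deflection comparison depends on what ends immersion. It is toward zero under the 10°C limit or a stop the drug leaves alone. It is absent, reversed or spurious if the drug alters tolerance.

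The size cannot be derived from the documents. Under the assumed SD, correlation and 3.6°C shift, the complete-pair estimate under the 10°C limit alone is attenuated by 4% when placebo deflection averages 21°C water and by 34% when it averages 13°C.

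Two further inferences should be resisted. The 35.5°C stop does not cost deflection points. No direction of bias can be given for the shivering endpoint, because it is scored as a core temperature and Section 2.2 asks only whether it is shifted.

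This is a cheap improvement to the analysis plan.

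**What to change.** In Section 12.0, Specific Aim 2:

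- **Primary endpoint.** Prespecify a paired analysis of the deflection point that keeps every participant and treats a point not reached as censored at the water temperature when immersion stopped. A censored-normal mixed model with a participant random effect would do, as would a paired rank test for censored data. State the criterion by which a visit is classed as not having reached the point.
- **Shivering.** Analyse onset in the same way on the water-temperature or time scale, which also matches the objective in Section 2.1 of delaying its onset. Report the core temperature at onset, among those who shiver, as descriptive.
- **Reporting.** Tabulate stops by reason and condition.
- **Sensitivity.** Keep the paired t-test on complete pairs as a sensitivity analysis.

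The cost is SAP wording and slightly more analysis. Core temperature and shivering are already measured continuously during immersion, and the water temperature at the stop is needed for the planned plot in any case. The downside is the assumption that the stop is uninformative given the model, to be examined with the stop-reason table and the sensitivity analysis. No stopping rule changes.
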